12.6.5 Concise Health Risk Tracking – Clinician Rated Module (CHRT-CR)

The CHRT-CR will be performed by the Medical Clinician only if a participant answers any of questions 14-16 on the CHRT-SR as Agree or Strongly agree as described above. This assessment will also include, as needed, more comprehensive risk assessment/safety planning provisions, as well as potentially hospitalization, following site-specific hospitalization protocols.

12.7 Substance Use Assessments

12.7.1 Timeline Follow-Back (TLFB)

The Timeline Follow-Back (Sobel & Sobel, 1992) procedure will be used to elicit the participant's self-reported use, quantity, and route of administration of substances at baseline, throughout the treatment period, and at end of treatment and follow-up assessments. At screening, this form will be used to assess substance use for the 30-day period prior to screening. The TLFB will be administered throughout the active treatment phase and through the end of the follow-up period to document the participant's self-reported use of substances for each day since the previous TLFB assessment. We plan to use the TLFB to track self-reported use of all substances. At the 12- and 16-week post-randomization follow-up, substance use is reported since the last visit.

12.7.2 Caffeine Intake Assessment

At screening, the Caffeine Intake Assessment will be modeled after the Supplemental Beverage Questions in use for the ABCD Study (Lisdahl et al., 2018). If a participant endorses use of any caffeinated beverages, they are then asked the typical number of caffeinated drinks they had per week in the past 30-days (covering categories of coffee, espresso, tea with caffeine, soda with caffeine, and energy drinks). A briefer version of the Caffeine Intake Assessment (Daily Caffeine Assessment) will be conducted prior to each rTMS/sham session (covering the past 24-hours) in a manner consistent with the FORM-90 approach.

12.7.3 DSM-5 Checklist

The DSM-5 (American Psychiatric Association, 2013) Checklist is a semi-structured, interviewer-administered instrument that provides current diagnoses for substance use disorders based on DSM-5 diagnostic criteria. The DSM-5 Checklist will be administered for each substance the participant reports using in the last 12 months (including cocaine and methamphetamine).

12.7.4 NIDA Cannabis Use Assessment

This survey assesses participants' recreational and medical cannabis/marijuana use frequency over the past 12 months, including reasons for use (e.g., to address medical/psychological

concerns, to replace other substances or medications), method of administration, and perceived harm or benefit associated with use. This form will be completed at screening.

12.7.5 Fagerström Test for Nicotine Dependence

The Fagerström Test for Nicotine Dependence (FTND) is used for assessing cigarette use and nicotine dependence (Heatherton et al., 1991) and will be administered to each participant at screening, at treatment week 4, end of treatment, and at each follow-up.

12.7.6 Cue Craving Assessment

The craving scale will assess current craving immediately following cue exposure, as well as after each rTMS/sham session. An additional item assessing ability to resist using is presented after each rTMS/sham session. This assessment will be performed immediately following cue presentation and at the end of each rTMS/sham session to make sure the participant is not experiencing significant craving before leaving the study site.

12.8 Daily Assessments

12.8.1 Daily Monitoring

To augment data collection in this trial, we will administer remote assessments/surveys to participants on their mobile devices through ePRO. Brief, electronic remote surveys will be administered to participants on day 1 of treatment and will occur daily until the week 16 follow-up time point (regardless of when the follow-up visit actually occurs). Data collection in-between study visits is critical for study outcomes and capturing an accurate picture of the recovery process. Remote surveys may also aid in retention of study participants and allow research members to more intensively follow-up with participants should they miss a survey (allowing for more potential contact with participants).

Remote surveys will be delivered to the participant's mobile phone as a survey invite link through an SMS text message (and via email). If participants do not have smartphones, one will be provided for use during the course of the study. Participants will also have the option to receive remote surveys via email. The survey invite includes an individualized link that contains embedded data. Participants will have 24 hours to complete the survey, up until the time the next survey is delivered. Responses will be date and time-stamped. In the case that two surveys are completed in the same day, the first survey of the day will be retained.

Two versions of the daily survey will be utilized, based on participant report of their primary stimulant substance(s) of abuse during screening: (1) primary cocaine; or (2) primary methamphetamines. The survey will ask participants to answer whether or not they used their primary reported substance of abuse (Yes/No); to rate their craving using a Visual Analog Scale; to rate their ability to resist use of primary substance on a Visual Analog Scale; to rate their overall mood on Visual Analog Scale; and to rate overall sleep quality on a Visual Analog Scale. Participants will receive the survey link at the same time each day, and be asked to report on the last 24 hours.

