17.6 Data Editing

Completed data will be entered into Advantage eClinical. If incomplete or inaccurate data are found, a query will be generated to the sites for a response. Sites will resolve data inconsistencies and errors and enter all corrections and changes into Advantage eClinical. Mobile survey data will be monitored for completeness and data quality to the extent possible as these self-reported assessments will be completed remotely by participants. As noted above, if participants complete more than one mobile survey within a 24 hour period, only the first entered for the day will be retained for analysis.

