7.7 Definition of the Exploratory Outcome Measures

Exploratory outcomes may include, and are not limited to:

- Other feasibility measures:
 - Percent of participants that complete all available questions for at least 75% of daily monitoring surveys (mobile questionnaires: MCQ, MMQ)
 - Expected once per day from Study Day 1 (randomization) to Study Day 112 (Week 16 follow-up visit target date)
 - If multiple surveys are completed, the first is retained for analysis
 - Percent of participants that complete all follow-up visits
- Self-reported cocaine and methamphetamine use (Timeline Follow-Back)
- Cocaine and/or methamphetamine craving (Visual Analogue Craving Scale, VAS, found on both CCA and MCQ/MMQ CRFs)
- Depression/anxiety symptoms (Hospital Anxiety and Depression Scale, HADS)
- Sleep quality (Actigraphy; Pittsburgh Sleep Quality Index, PSQI)
- Quality of life (Health Related Quality of Life, HRQOL-4)

- Impact of personal characteristics (age, handedness) on treatment outcomes
- Cognitive Behavioral Therapy (CBT) participation (Dynamicare dataset)
- Motor threshold changes over the treatment course (TMS; Machine output)

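### The first-survey-of-the-day rule can drop on-time answers to a different daily survey, which can only lower the exploratory 75% monitoring rate if that rate counts retained surveys

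*Protocol*

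**What the plan says.** Protocol 12.8.1 (Daily Monitoring) sets the delivery schedule and recall period: "Participants will receive the survey link at the same time each day, and be asked to report on the last 24 hours". The clock time of delivery is not given. The response window is stated as: "Participants will have 24 hours to complete the survey, up until the time the next survey is delivered". Responses carry a date and time stamp, and each invitation has an individualised link with embedded data. The retention rule is: "In the case that two surveys are completed in the same day, the first survey of the day will be retained".

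Protocol 17.6 (Data Editing) refers back to that rule and words it slightly differently: "if participants complete more than one mobile survey within a 24 hour period, only the first entered for the day will be retained for analysis".

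SAP 7.7 defines the feasibility measure as: "Percent of participants that complete all available questions for at least 75% of daily monitoring surveys". It expects one survey per day from Study Day 1 to Study Day 112. Beneath that it adds: "If multiple surveys are completed, the first is retained for analysis".

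Protocol 2.5 sets a 75% target for this measure and says that it will inform the decision on a larger trial.

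**The concern.** The response window and the retention rule work on different clocks. The window runs from one delivery to the next. The retention rule works by day of completion. Unless delivery is at about midnight, every window spans two calendar dates. A participant can answer yesterday's survey this morning and today's survey tonight. Both answers are on time and belong to different invitations, yet the text keeps only the first.

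No section limits the rule to repeat answers to one invitation, ties a response to its delivery, or says that a dropped on-time survey still counts as completed. A programmer who follows the text would delete valid records. At stake are the exploratory monitoring rate and the daily records of use, craving, ability to resist, mood and sleep.

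**Working it through.** **Inputs from the documents.** 24-hour window, closing at the next delivery (Protocol 12.8.1). First survey of the day kept (Protocol 12.8.1 and 17.6). Expected surveys on Study Days 1 to 112, with a participant threshold of 75% (SAP 7.7).

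**Inputs assumed.** The next-day share q, meaning the probability that a survey is answered on the calendar date after delivery. The completion probability c. Independence of timing and completion from one survey to the next. The 75% measure is taken to count retained surveys.

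**The plan's own figure.** 16 weeks × 7 days = 112 expected surveys, as in SAP 7.7. The threshold is 0.75 × 112 = 84, so at most 112 − 84 = 28 may be missed or dropped.

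**When a survey is dropped.** Survey k, answered on time, is completed on date k or date k+1. It is lost when survey k−1 is completed on date k and survey k is completed on date k too. There are 111 consecutive pairs, and each gives a loss with probability c²q(1−q). So

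expected number retained = 112c − 111c²q(1−q).

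**Fully compliant participant (c = 1).** Without the rule, 112 of 112 are kept.

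| q | Expected retained | Share of 112 | Probability below 84 (simulated) |
|---|---|---|---|
| 0.1 | 112 − 111 × 0.09 = 102.0 | 91% | about 0% |
| 0.2 | 112 − 111 × 0.16 = 94.2 | 84% | 0.02% |
| 0.3 | 112 − 111 × 0.21 = 88.7 | 79% | 4% |
| 0.5 | 112 − 111 × 0.25 = 84.3 | 75.2% | 39% |

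The results are symmetric about q = 0.5, which is the worst value under independence.

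**Participant who completes 90% on time (c = 0.9).** Without the rule, the expected number is 100.8 and the probability of reaching 84 is 1.00.

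| q | Expected retained | Probability of at least 84 (simulated) |
|---|---|---|
| 0.1 | 100.8 − 111 × 0.81 × 0.09 = 92.7 | 0.99 |
| 0.2 | 100.8 − 111 × 0.81 × 0.16 = 86.4 | 0.79 |
| 0.3 | 100.8 − 111 × 0.81 × 0.21 = 81.9 | 0.32 |
| 0.5 | 100.8 − 111 × 0.81 × 0.25 = 78.3 | 0.05 |

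The probabilities come from simulations of at least 20,000 participants with 112 surveys each. The simulated means agree with the formula.

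**Extremes.** Always answering on the delivery date, or always on the next date, keeps 112 of 112. Strict alternation (next day, same day, next day, and so on) keeps 56 of 112, or 50%, with every survey answered on time.

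**The case against.** **The rule may be meant only for duplicates.** SAP 7.7 does not mention a completion date. Its sentence sits under an expectation of one survey per day and can be read as covering repeat answers to one expected survey. That is fair for the SAP taken alone. It does not help Protocol 12.8.1 and 17.6, which speak of two surveys in the same day, and nothing restricts those sections to repeats.

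**Completed is not the same as retained.** The measure counts surveys that participants complete, while the rule governs what is kept for analysis. The two could be separated, but the documents do not do so, and SAP 7.7 puts the rule beneath the measure. This stands as an assumption behind the figures.

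**One record per day may guard against overlap.** Participants report on the last 24 hours. If recall runs back from the moment of completion, a 9 am and a 7 pm answer on one date share 14 hours. This stands as a reason for care in dating answers. It does not justify recording an on-time response as missing.

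**Stronger readings that the documents do not support.**

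- A reader might infer that surveys never sent are counted as missed, because surveys start on day 1 of treatment while the SAP counts from randomisation. SAP 3.2.1 and 3.2.3 make Study Day 1 the day of randomisation and start the treatment period on that day. SAP 2.2.2.2 lists the daily questionnaire among the assessments that may be completed after randomisation. No section says that surveys wait for the first stimulation session.
- A reader might take the 24-hour wording in Protocol 17.6 as a rolling rule that drops any survey completed less than 24 hours after the last one kept. Under random response times that would keep only about 63%. But the sentence refers back to the earlier rule and ends with the day as its unit: "only the first entered for the day will be retained for analysis". It is better read as a restatement.
- A reader might infer that fully compliant participants will commonly miss the target. Under independent timing that is so only when answers are split fairly evenly between same day and next day.

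**Conclusion.** The inconsistency is real on the text of Protocol 12.8.1 and 17.6. For any delivery time away from midnight, valid on-time answers can be deleted. If the 75% measure counts retained surveys, the error runs in one direction only, towards understating monitoring compliance.

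Its size cannot be fixed from the documents, because the delivery time, the next-day share and the dependence between days are all unstated. It ranges from no loss for consistent responders to half of all surveys under strict alternation. Participants who already miss some surveys are the most exposed, since those misses use up part of the allowance of 28.

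The affected measure is exploratory, its analysis is optional under SAP 7.8, and SAP Table 1 assigns it to the Lead Node. The primary outcome (at least 20 sessions) and the secondary urine drug screen outcome are not touched. The point deserves correction because the measure has a stated target and is meant to inform a larger trial.

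**What to change.** 1. In Protocol 12.8.1 and 17.6, limit the first-kept rule to repeat responses to the same individualised survey link. Say the same explicitly in SAP 7.7, so that all three sections agree.
2. In SAP 7.7, state that every on-time response to a distinct invitation counts as completed for the 75% measure, provided that all available questions are answered.
3. Keep both the send time and the completion time for each response. State how the 24-hour recall period is dated, since assigning a late answer to its send date could misplace the behaviour it describes.
4. State the delivery time. Because each window closes when the next opens, the delivery time and the completion stamp together identify the invitation, even if the link itself does not.

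The cost is a few lines of wording and a small change to one derivation, with no added participant burden. Links with embedded data and time stamps are already part of the system. If the database keeps the dropped responses in raw form, the measure can be re-derived and reported under both rules. If they were not kept, the report should say that the rate may be understated.

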12.8.2 Actigraphy

The ActiGraph GT9X Link wristband device will be used to collect participants' daily sleep data. Information obtained from the device includes, but is not limited to, sleep latency, sleep duration, and intervals of waking during the sleep period. Participants will be provided with the device and necessary accessories for wear and battery charging. Data will be extracted from the device by research staff during study visits.

12.9 Lab Testing And Samples

12.9.1 Urine Drug Screen for Other Substances

To assess the efficacy outcome, Urine Drug Screens (UDS) will be collected at screening, randomization, at each treatment session prior to beginning the rTMS/sham treatment, at the end of treatment visit and follow-up visits (UDS will be omitted if follow-up visits are performed remotely). All urine specimens will be collected using FDA-approved one-step temperature-controlled urine drug test cups following all of the manufacturer's recommended procedures. Urine drug screen (UDS) testing will be performed using a FDA cleared for use one-step urine drug dip card following the manufacturer's recommended procedures. Single dipsticks will be used for fentanyl testing. Fentanyl dipsticks are not FDA cleared, therefore, results cannot be used for clinical care. Results can only be used to add to the study database to characterize a study population. The UDS will test for the presence of the following drugs: opioids, oxycodone, barbiturates, benzodiazepines, cocaine, amphetamine, methamphetamine, marijuana, methadone, buprenorphine, phencyclidine (PCP), fentanyl and ecstasy (MDMA). In the event urine specimen tampering is suspected, either based on the observation or the adulterant tests, research staff should request a second urine sample and may observe the urine collection process according to clinic standard operating procedures. A further validity check is performed using a commercially available adulterant test strip.

12.9.2 Urine Pregnancy Test

A urine pregnancy test will be conducted at screening to determine eligibility for study procedures. If the test is positive, no further procedures will be conducted, and the participant will be excluded from study procedures. If screening and randomization do not occur on the same day, urine pregnancy test will be repeated before randomization procedure. Additional urine pregnancy tests will be administered prior to the first visit of treatment week 4 and treatment week 8. If positive, women will no longer receive the rTMS intervention. Pregnancy will be followed through resolution. Women will need to agree to use an appropriate form of birth control throughout the treatment phase of the study.

13.0 TRAINING REQUIREMENTS

13.1 Overall

A comprehensive Training Plan will be developed to incorporate general training, study-specific training, mechanisms for competency assessment as well as a detailed description of training, supervision, and fidelity monitoring procedures. The Investigative Team is responsible for the development of a comprehensive Training Plan, instructional material, and delivery of the training, with the team comprised of the Lead and Co-Lead Nodes, CCC, DSC, as well as other participating nodes and subject matter experts, as applicable. Remote training will be conducted as possible, including training in rTMS and EEG monitoring (where applicable).

The CTN-0108 research staff will be trained as specified in the study Training Plan. Training will include Human Subjects Protection (HSP) and Good Clinical Practice (GCP) as well as protocol-specific training on assessments, study interventions, safety and safety event reporting, study visits and procedures, data management, quality assurance, laboratory procedures, etc. The Lead Node is primarily responsible for development and delivery of study-specific training related to the study intervention(s) and procedures. The CCC is responsible for the development and delivery of non-intervention training, including regulatory and laboratory procedures, safety and safety event reporting, quality assurance and monitoring, etc. The DSC is responsible for training related to data management (DM), the electronic data capture system, and good clinical DM practices. Other parties will contribute as needed based on the subject matter and material to be covered. The various sub-teams will collaborate to deliver quality instructional material designed to prepare research staff to fully perform study procedures based on the assigned research roles and responsibilities.

In addition to general and study-specific training, the Training Plan will include a description of the delivery methods to be used for each training module (e.g., via self-study, online, webcast, or teleconference). Research staff are required to complete institutionally required training per their research site, Institutional Review Board(s), and authorities with regulatory oversight. Tracking of training completion for individual staff as prescribed for assigned study role(s) will be documented, endorsed by the site Principal Investigator and the Lead Node, and audited by the CCC. As changes occur in the prescribed training, the Training Plan and training documentation tracking forms will be amended to reflect these adjustments.

13.2 rTMS Training and Supervision

All sites must have experience in the delivery of rTMS. Site Operating Procedures (SOPs) for the use of the MagVenture MagPro X100 system and the Provider Manual will be provided to research staff. Training will be provided for study-specific rTMS procedures by the certified rTMS Investigative Team member and reviewed quarterly. Additionally, rTMS Operators, rTMS Advanced Operators, and Site PIs will be trained by MagVenture in the administration of rTMS using their equipment and receive a MagVenture Certification of Completion. At each site, the Medical Clinician will supervise (as defined in the MOP) the rTMS delivery.

14.0 CONCOMITANT THERAPY/INTERVENTION

14.1 General

Individuals are not allowed to engage in any other treatments specifically targeting their substance use disorder, other than the study provided CBT app, because this could interfere with the ability to detect the effect of rTMS. Study participants may engage only in self-help group activities (e.g., Alcoholics Anonymous, Narcotics Anonymous, SMART Recovery) focused on their substance use disorder. However, participants may engage in treatments targeting other psychiatric disorders.

14.2 Medications Prohibited/Allowed During Trial

Anticonvulsants and/or benzodiazepines can raise the seizure threshold and interfere with the efficacy of rTMS. Participants who are prescribed anticonvulsants or benzodiazepines must be on a stable dose for at least 4 weeks prior to consent. Medications will be assessed as part of the standard medical assessments (see Table 5 in Section 12) at screening, each treatment session, end of treatment visit (if applicable), as well as 12- and 16-week follow-up visits.

15.0 STATISTICAL DESIGN AND ANALYSES

15.1 General Design

15.1.1 Study Hypotheses

The primary hypothesis for this trial relates to feasibility:

Primary (Feasibility) Hypothesis: More than 75% of all participants randomized in CTN-0108 will receive 20 or more rTMS sessions.

The secondary hypothesis for this trial relates to efficacy. It is stated separately for MUD and CUD for clarity.

Secondary (Efficacy, CUD) Hypothesis: Individuals who enroll with primary CUD and receive active rTMS will have a significantly higher percentage of weekly negative UDS results over the course of treatment, as compared to those in the sham group.

Secondary (Efficacy, MUD) Hypothesis: Individuals who enroll with primary MUD and receive active rTMS will have a significantly higher percentage of weekly negative UDS results over the course of treatment, as compared to those in the sham group.

